4.1. Changes from Analyses Specified in the Protocol

The protocol states that the number of days free of mechanical ventilation at Day 29 will be compared between treatment groups using an analysis of covariance (ANCOVA), adjusting for age, and randomization stratification factor, *among survivors*. This has been clarified in [Section 7.2.2.1](#) of this SAP to be the number of days alive and free of mechanical ventilation; this represents a composite strategy for handling the intercurrent event of death.

The same modification applies to the duration of ICU stay at Day 29 *among survivors*, as well duration of hospitalization at Day 29 *among survivors*. These have been clarified in [Sections 7.2.2.2](#), [7.2.2.5](#), [9.4.5.2](#) and [9.4.5.3](#) of this SAP to be the number of days alive and not in the ICU and the number of days alive and not hospitalized, again representing a composite strategy for handling the intercurrent event of death.

Additional changes from the protocol are items 1, 2, and 4 given below in [Section 4.2](#) of this SAP. The analyses as specified in this SAP over-ride the protocol.

4.2. Changes from Analyses Specified in the Previous Version of the SAP

1. The definition of Day 1 has been updated for patients randomized but not dosed with ravulizumab as the later of the date of randomization or the date of the Day 1 visit. This is to allow time for Day 1 assessments to occur on the following calendar day, but within 24 hours of randomization, for patients in the ICU, and to better align with the definition of Day 1 for patients randomized and dosed with ravulizumab (the date of the first infusion of ravulizumab).
2. Missing data sensitivity analyses for the primary endpoint have been added to [Section 7.2.1.1](#) as per feedback from health authorities and will include imputing any missing data assuming death, assuming survival, and performing a tipping point analysis.
3. For the sensitivity analyses of the primary endpoint using a 3-level categorical outcome and a logistic regression model, clarified in [Section 7.2.1.1](#) that the missing data for these analyses will be imputed as for the primary analysis using a multiple imputation approach assuming the data are missing at random (MAR) and using a logistic regression model with covariates for treatment group, the randomization stratification factor, age, sex and presence of a pre-existing condition at baseline.
4. In [Section 7.2.2.1](#), clarified that the number of days free of mechanical ventilation at Day 29 will be summarized by treatment group for all patients and by mortality and added a tipping point sensitivity analysis. These changes also apply to [Sections 7.2.2.2](#) and [7.2.2.5](#) for the durations of ICU stay and hospitalization.
5. In [Sections 7.2.2.3](#) and [7.2.2.4](#), added that for patients who die, remaining values up to Day 29 will be imputed as the worst possible value, representing a composite strategy for handling the intercurrent event of death.
6. For the exploratory endpoint of progression to renal failure, explained in [Section 7.2.3.1](#) that deaths will be assumed to be failures (a composite strategy for handling the intercurrent event of death) and that other missing data will be handled as described for the primary analysis of the primary endpoint.

The SAS code in [Appendix 9.5.2](#) has been updated to align with specified analysis methods as described in this SAP. Additional administrative changes have been made for accuracy, clarity and consistency.

5. DEFINITIONS

5.1. Efficacy

5.1.1. Primary Endpoint

The primary efficacy endpoint is survival (based on all-cause mortality) at Day 29.

5.1.2. Secondary Endpoints

The secondary efficacy endpoints at Day 29 are:

- Number of days free of mechanical ventilation
- Duration of intensive care unit (ICU) stay
- Change from baseline in Sequential Organ Failure Assessment (SOFA) score
- Change from baseline in SpO₂/FiO₂
- Duration of hospitalization

An additional secondary endpoint will be assessed beyond Day 29:

- Survival (based on all-cause mortality) at Day 60 and Day 90

5.1.2.1. Mechanical Ventilation

The number of days free of mechanical ventilation is defined as the total number of days from Day 1 to Day 29 without invasive or non-invasive mechanical ventilation.

5.1.2.2. SpO₂/FiO₂

Oxygenation will be measured using the peripheral capillary oxygen saturation level (SpO₂) and the amount of supplemental oxygen as measured by the fraction of inspired oxygen (FiO₂) received by taking the ratio of these 2 measures at the same time point.

5.1.2.3. Duration of ICU Stay

The duration of ICU stay is defined as the total number of days from Day 1 to Day 29 that the patient is in the ICU.

5.1.2.4. SOFA Score

Multiple organ failure is a significant indicator of mortality in patients admitted to the ICU. In this study, patients will be evaluated using the SOFA score, an assessment tool that includes a review of 6 organ systems: respiratory, renal, hepatic, cardiac, coagulation, and central nervous system ([Vincent, 1998](#)). Each organ system is scored from 0 to 4 points using the worst value observed within the previous 24 hours ([Table 2](#)). The total score ranges from 0 to 24, with a higher score indicating a worse condition.

Arterial blood gas may not be drawn on a protocol specified visit day; therefore, the assessment of partial pressure of oxygen (PaO₂) is optional and the highly correlated SpO₂ will be a surrogate for the respiratory system assessment.

Table 2: Sequential Organ Failure Assessment Scoring

Organ System	Variable (Units)	Score Allocation				
		0	1	2	3	4
Respiratory	PaO ₂ /FiO ₂ (mmHg) ¹	≥ 400	< 400	< 300	< 200 AND respiratory support (eg, mechanical ventilation)	< 100 AND respiratory support (eg, mechanical ventilation)
	SpO ₂ /FiO ₂	≥ 302	< 302	< 221	< 142 AND respiratory support (eg, mechanical ventilation)	< 67 AND respiratory support (eg, mechanical ventilation)
Renal	Creatinine (μmol/L)	< 110	110 - 170	171 - 299	300 - 400	> 440
Hepatic	Bilirubin (μmol/L)	< 20	20 - 32	33 - 101	102 - 204	> 204
Cardiac	Inotropes (μg/kg/min)	Mean arterial pressure > 70 mm Hg	Mean arterial pressure < 70 mm Hg	Dopamine ≤ 5 or Dobutamine any dose	Dopamine > 5 or Epinephrine ≤ 0.1 or Norepinephrine ≤ 0.1	Dopamine > 15 or Epinephrine > 0.1 or Norepinephrine > 0.1
Coagulation	Platelets (× 10 ³ /mm ³)	≥ 150	< 150	< 100	< 50	< 20
CNS	GCS	15	13 - 14	10 - 12	6 - 9	< 6

¹ As arterial blood gas may not be drawn on a protocol-specified visit day, the PaO₂ assessment is optional. Abbreviations: CNS = central nervous system; GCS = Glasgow Coma Scale; FiO₂ = fraction of inspired oxygen; PaO₂ = partial pressure of oxygen; SpO₂ = peripheral capillary oxygen saturation. Source: [Vincent, 1998](#); [Pandharipande, 2006](#)

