### 1.3. Schedule of Activities

**Table 1: Schedule of Activities**

Period	Screening Period	Primary Evaluation Period							Follow-up Period 	
		D1 	D5 	D10 	D15 	D22	D29/ Discharge 	Early Termination 	D60	D90
Study Day (D)	D -3 to D -1									
Study Window (days)	NA	NA	±1	±1	±1	±1	±1		±7	
Eligibility										
Informed consent	X									
Inclusion/exclusion	X									
Medical history 	X									
Demographics	X									
Study Administrative										
Confirmation of vaccination or appropriate antibiotic prophylaxis against N. meningitidis 	X								X	
Screening Laboratory Tests										
Confirmed positive SARS-CoV-2 test	X									
Chest CT or X-ray 	X									
Pregnancy test 	X						X	X		
Randomization										
Randomized to study drug + BSC or BSC alone		X								
Administration of Study Drug										
Ravulizumab 		X	X	X	X					
Efficacy Assessments										
Survival status										X
Mechanical ventilation status	X									
Hospitalization status										
Intensive care unit status										
Dialysis status										
FiO 2 , SpO 2 , PaO 2 										
Sequential Organ Failure Assessment score	X	X	X	X	X	X	X	X	X	
Safety Assessments										
Electrocardiogram	X						X	X		
Complete physical examination 	X						X	X		
Abbreviated physical examination 		X	X	X	X	X				
Glasgow Coma Scale	X	X	X	X	X	X	X	X		

Period	Screening Period	Primary Evaluation Period							Follow-up Period 	
		D1 	D5 	D10 	D15 	D22	D29/ Discharge 	Early Termination 	D60	D90
Study Day (D)	D -3 to D -1									
Study Window (days)	NA	NA	±1	±1	±1	±1	±1			±7
Body weight	X	X	X	X	X					
Vital sign measurements (predose) 	X	X	X	X	X	X	X	X		
Adverse event review and evaluation	X	<<monitor continuously>>								X
Review safety card 		X 					X 	X 		X 
Safety Laboratory Tests (Predose)										
Clinical chemistry	X	X	X	X	X	X	X	X		
Hematology	X	X	X	X	X	X	X	X		
Coagulation panel and D-dimer	X	X	X	X	X	X	X	X		
Urinalysis	X	X	X	X	X	X	X	X		
Direct Coombs test	X									

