5.1.3.1. Renal Failure

Progression to renal failure will be assessed based on whether a patient required dialysis.

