7.2.2. Secondary Analyses

A closed testing procedure will be applied to control the type I error for the analyses of the primary and secondary endpoints at Day 29. If the primary endpoint is statistically significant in favor of ravulizumab, the secondary endpoints will be evaluated according to the following rank order:

1. Number of days free of mechanical ventilation at Day 29,
2. Duration of ICU stay at Day 29,
3. Change from baseline in SOFA score at Day 29,
4. Change from baseline in SpO₂/FiO₂ at Day 29,
5. Duration of hospitalization at Day 29.

The hypothesis testing will proceed from highest rank (#1) the number of days free of mechanical ventilation at Day 29 to the lowest rank (#5) duration of hospitalization at Day 29, and if statistical significance is not achieved at an endpoint ($p \geq 0.05$), then endpoints of lower rank will not be considered to be statistically significant. Confidence intervals and p-values will be presented for all secondary efficacy endpoints for descriptive purposes, regardless of the outcome of the closed testing procedure.

An additional secondary endpoint will be assessed beyond Day 29 regardless of the results of the closed testing procedure: Survival (based on all-cause mortality) at Day 60 and Day 90.

The PPS will be used in a sensitivity analysis for all secondary efficacy endpoints.

7.2.2.1. Number of Days Free of Mechanical Ventilation at Day 29

The number of days free of mechanical ventilation at Day 29 will be summarized by treatment group for all patients and by mortality. The number of days free of mechanical ventilation at Day 29 will be compared between treatment groups using an analysis of covariance (ANCOVA), adjusting for age and the randomization stratification factor, among survivors (ie, the number of days alive and free of mechanical ventilation).

Missing data will be imputed using a multiple imputation approach assuming the data are MAR and using a regression model with covariates for treatment group, the randomization stratification factor, age, sex and presence of a pre-existing condition at baseline (diabetes mellitus, obesity, respiratory condition, and/or coronary artery disease). Sensitivity analyses will include:

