Changes in SOFA score will be analyzed using a restricted maximum likelihood (REML)-based repeated measures approach (i.e. MMRM, [Mallinckrodt, 2008](#)) and all available longitudinal data. The model will include fixed effects for baseline SOFA score, age, randomization stratification factor, treatment group indicator, study day (Day 5, 10, 15, 22, 29), and study day by treatment group interaction. An unstructured covariance structure will be used to model the within patient errors. If this analysis fails to converge, the following structures will be tested and the final covariance structure will be determined by Akaike's information criterion (AIC): first-order autoregressive, compound symmetry, and Toeplitz. The Kenward-Roger approximation will be used to estimate denominator degrees of freedom. For patients who die, remaining values up to Day 29 will be imputed as a score of 24, the worst possible value.

A sensitivity analysis will be performed using a missing not at random (MNAR) mechanism for the missing data, where it will be assumed that unobserved outcomes for patients who discontinue early from the ravulizumab + BSC group will follow the trajectory of outcomes similar to the control group (BSC alone), taking into account observed values prior to discontinuation ([O'Kelly and Ratitch, 2014](#)). Patients discontinuing early from the BSC alone group will be assumed to have outcomes similar to the BSC alone patients who remain on their randomized treatment. Refer to [Appendix 9.5.2.2.2](#) for additional details.

7.2.2.4. Change from baseline in SpO₂/FiO₂ at Day 29

Changes in SpO₂/FiO₂ from Day 1 to Day 29 will be summarized daily by treatment group for all patients and by mortality.

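### The renal SOFA item uses creatinine alone with no rule for dialysis, so renal failure is understated in dialysed survivors on the rank 3 secondary endpoint

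*SAP*

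**What the plan says.** SAP 5.1.2.4 gives the scoring rule: "Each organ system is scored from 0 to 4 points using the worst value observed within the previous 24 hours". It adds: "The total score ranges from 0 to 24, with a higher score indicating a worse condition". Protocol 8.3.2.1 has the same scoring rule. In SAP Table 2 and Protocol Table 7 the renal row is a set of creatinine bands (below 110, 110 to 170, 171 to 299, 300 to 400, above 440 μmol/L for scores 0 to 4). Neither table has a dialysis or urine-output criterion.

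Elsewhere dialysis is the trial's marker of renal failure. SAP 5.1.3.1 says: "Progression to renal failure will be assessed based on whether a patient required dialysis". The Schedule of Activities lists "Dialysis status" among the efficacy assessments.

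The endpoint "Change from baseline in SOFA score at Day 29" is third of five in the closed testing order (SAP 7.2.2, Protocol 9.4.1.3). On the method, SAP 7.2.2.3 says: "Changes in SOFA score will be analyzed using a restricted maximum likelihood (REML)-based repeated measures approach". The model uses Days 5, 10, 15, 22 and 29. The only intercurrent event given a rule is death: "For patients who die, remaining values up to Day 29 will be imputed as a score of 24, the worst possible value". The sensitivity analysis in that section concerns missing data after discontinuation. A dialysed patient who is alive has an observed creatinine, so neither rule applies.

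**The concern.** Dialysis removes creatinine. This is general knowledge, not a statement in the documents. While dialysis continues, the value entering the score reflects the treatment as well as the kidney. A patient who counts as a renal failure under SAP 5.1.3.1 can therefore score 0 or 1 on the renal item under SAP 5.1.2.4.

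The 24-hour worst-value rule helps only when an undialysed value falls in the window. Under continuous or regular dialysis there may be none.

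SOFA change is tested confirmatorily if survival and ranks 1 and 2 succeed, and it gates ranks 4 and 5. Treatment is open-label, so the decision to dialyse is made with the arm known. A difference between arms in dialysed survivors would enter the SOFA comparison with the wrong sign: more dialysis would lower the score.

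**Working it through.** The documents state no SD, effect size, power or dialysis rate for SOFA, so there is no figure of the plan to reproduce. The 243 patients rest on survival and are not affected.

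**Step 1. Single patients.** Bands are from Table 2. Creatinine values are illustrative, and each patient's renal state while dialysed is taken as score 4.

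| Patient | Baseline score | Day 29 score as written | Recorded change | Change if dialysed = 4 |
|---|---|---|---|---|
| A: 200 at baseline; 150 on dialysis at Day 29 | 2 | 1 | 1 − 2 = −1 | 4 − 2 = +2 |
| B: 100 at baseline; 150 on dialysis at Day 29 | 0 | 1 | 1 − 0 = +1 | 4 − 0 = +4 |
| C: 150 on dialysis at both times | 1 (4 if dialysed = 4) | 1 | 1 − 1 = 0 | 4 − 4 = 0 |
| D: 150 on dialysis at baseline; 200 off dialysis at Day 29 | 1 (4 if dialysed = 4) | 2 | 2 − 1 = +1 | 2 − 4 = −2 |

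A and B are each understated by 3 points. Only A looks like an improvement; B still records a worsening. In C the errors cancel and in D they reverse. The maximum is 4 points (score 0 recorded, 4 underlying), or 4 of 24.

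Patients like C and D are possible: SAP 7.2.3.1 restricts the exploratory renal analysis to those not on dialysis at Day 1.

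**Step 2. One arm.** Mean understatement at a visit = share of the arm alive and on dialysis × points masked. With assumed shares of 5% to 20% and 1 to 4 points: 0.05 × 1 = 0.05 up to 0.20 × 4 = 0.8 points.

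**Step 3. Difference between arms.** Ignoring baseline masking and with equal masking per dialysed patient, the shift in ravulizumab minus BSC = (share on BSC − share on ravulizumab) × points. A positive shift counts against ravulizumab.

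| Assumed share BSC / ravulizumab | 1 point | 2 points | 4 points |
|---|---|---|---|
| 10% / 5% | +0.05 | +0.10 | +0.20 |
| 20% / 10% | +0.10 | +0.20 | +0.40 |
| 5% / 10% | −0.05 | −0.10 | −0.20 |
| 10% / 20% | −0.10 | −0.20 | −0.40 |

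With equal shares and equal masking the shift is 0.

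**Step 4. Equal dialysis rates among survivors are not enough.** Deaths score 24, so only living patients are masked. Take the planning survival of 80% and 60% (SAP 9.3) and an assumed 15% of survivors dialysed in each arm. The shares are 0.80 × 0.15 = 12% and 0.60 × 0.15 = 9%. With 2 to 4 points the shift is (0.09 − 0.12) × 2 = −0.06 to (0.09 − 0.12) × 4 = −0.12, in favour of ravulizumab.

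**Step 5. Scale against deaths.** If survivors have the same mean SOFA *s* in both arms, deaths contribute (difference in mortality) × (24 − *s*). At the planned difference with assumed *s* of 4 to 10: 0.20 × 20 = 4.0 to 0.20 × 14 = 2.8 points. The smallest significant survival difference at 162/81 is about 1.97 × √(0.733 × 0.267 × (1/162 + 1/81)) = 0.12. There the contribution is 0.12 × 20 = 2.4 to 0.12 × 14 = 1.7 points. The largest shift in Step 3 is at most about 0.4 / 1.7 = 24% of this.

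**The case against.** The strongest case against is that this is a minor clarification.

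- **Published scale.** Both tables cite published sources, and Protocol Table 4 calls SOFA a validated endpoint. The hepatic and coagulation items also use laboratory values alone. Respiratory support earns no points by itself; it is a co-condition for scores 3 and 4. Only the cardiac item scores treatment directly. This stands: the renal row is not a lone anomaly. It does not answer how to score a creatinine held down by the support the trial uses to define renal failure.
- **Small beside deaths.** Rank 3 is reached only after a significant survival benefit, and Step 5 shows deaths scored as 24 are likely to dominate. This stands, and limits the weight of the point.
- **Dialysis is reported separately.** SAP 7.2.3.1 analyses progression to dialysis, counting deaths as failures, and time to progression. An imbalance could be seen there, but an exploratory endpoint does not correct a confirmatory one.
- **A fixed score of 4 has its own weakness.** It makes the item follow an open-label decision: creatinine 200 (score 2) becomes 4 once dialysis starts. This stands and is why both scores should be shown.

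A reader might infer that dialysis is generally counted as organ recovery. The endpoint is change from baseline, and patient B shows that a dialysed patient can still record a worsening. A reader might also infer a bias against ravulizumab, or one favouring it. The documents support neither: Steps 3 and 4 give shifts of both signs from different assumptions.

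**Conclusion.** The point holds as a gap in endpoint scoring. Followed exactly, the plan can give a living patient in dialysis-dependent renal failure a renal score of 0 or 1. The error is up to 4 of 24 points at an assessment. In the change score it is usually understated deterioration, but it can cancel or reverse for patients dialysed at Day 1.

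The treatment comparison is distorted when the share alive and on dialysis, or the masking per patient, differs between arms. The size is about 0.05 to 0.4 points for assumed arm differences of 5 to 10 percentage points and 1 to 4 masked points. The direction is unknown. All dialysis rates and masked points are assumptions.

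The primary endpoint, its sample size and ranks 1 and 2 are untouched. It does not follow that a significant rank 3 result would be invalid. The case for acting is that the score is wrong by the plan's own marker of renal failure and the correction is cheap.

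**What to change.** In SAP 5.1.2.4 and Table 2, and in Protocol Table 7 to match, add an endpoint-scoring rule: the renal item is set to 4 at any SOFA assessment, baseline included, if the patient is on an ongoing course of dialysis (continuous or intermittent, including days between sessions) or has received dialysis within the 24-hour scoring window. Derive it from the dialysis status already collected. Report the analysis with the creatinine-only score as a sensitivity analysis, so that the effect of the rule is visible. This changes no patient care.

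The cost is one sentence in each document, one derivation line and one repeated analysis. The available text of the Schedule of Activities does not show how often dialysis status is recorded, so confirm that the case report form identifies a course of dialysis, not only its first date. There are two downsides: the item then depends on an open-label decision to dialyse, and patients on dialysis throughout carry a fixed renal score of 4.

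While the row is open, reconcile its top two bands: creatinine from 401 to 440 μmol/L has no score in either table.

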5.1.2.5. Duration of Hospitalization

The duration of hospitalization is defined as the total number of days from Day 1 to Day 29 that the patient is in the hospital.

5.1.3. Exploratory Endpoints

The exploratory efficacy endpoints are:

- Incidence of progression to renal failure requiring dialysis at Day 29
- Time to clinical improvement (based on a modified 6-point ordinal scale) over 29 days
- SF-12 Physical Component Summary (PCS) and Mental Component Summary (MCS) scores at Day 29 (or discharge), Day 60 and Day 90
- EQ-5D-5L scores at Day 29 (or discharge), Day 60 and Day 90

5.1.3.1. Renal Failure

Progression to renal failure will be assessed based on whether a patient required dialysis.

5.1.3.2. Clinical Improvement

Time to clinical improvement will be evaluated during this study and is defined as a live discharge, a decrease from of least 2 points (ie, #5 to #3) from baseline, or both. A modified 6-category ordinal scale (itemized below) will be used to evaluate clinical improvement.

1. Discharged
2. Hospitalized, not requiring supplemental oxygen
3. Hospitalized, requiring supplemental oxygen
4. Hospitalized, requiring noninvasive mechanical ventilation
5. Hospitalized, requiring invasive mechanical ventilation
6. Death

5.1.3.3. 12-item Short Form PCS and MCS Scores

The Short-Form (SF)-12, version 2 (1-week recall period) is a validated health-related quality of life (HR-QOL) instrument that is widely used across a broad spectrum of disease indications. The SF-12 survey contains 12 questions and covers 8 domains. There is a further stratification into 2 summary measures (Physical Component Summary [PCS] and Mental Component Summary [MCS]) as specified below. The summary measures are scored using a norm-based method (ie, mean = 50, SD = 10), where a score of 50 indicates an average score with respect to a healthy population. Higher scores indicate better quality of life.

- PCS: general health (1 item), physical functioning (2 items), role physical (2 items) and body pain (1 item)
- MCS: vitality (1 item), social functioning (1 item), role emotional (2 items) and mental health (2 items)

The survey is anticipated to be completed in several minutes and can be completed by the patient or via an interviewer (in-person or over the telephone).

